In the Epizyme-sponsored pediatric phase I trial, one child developed T-cell lymphoblastic lymphoma (T-LBL) after receiving tazemetostat for 14 months. As of 1 May 2018, this is the only case of T-cell lymphoma that has occurred out of a total of 79 children enrolled in tazemetostat clinical trials. In addition, there have been no cases of T-LBL or related T-acute lymphoblastic leukemia (T-ALL) in the 702 adult patients treated across multiple studies conducted in different types of cancer. All tazemetostat trials were temporarily halted while a risk assessment was conducted. Pediatric patients were noted to have higher tazemetostat exposures than had been seen in adults (specifically high AUC (0-24h)). In the company's assessment, the risk for T-LBL/T-ALL in tazemetostat clinical trials appears to be largely concentrated in pediatric patients based on:

- 1) The known epidemiology / pathophysiology of T-LBL/ALL.
- 2) Age-related intact and active thymus (thymic involution increases over time with reduced risk with increasing age)
- 3) Higher AUC (0-24h) exposures in pediatric patients

Based on these data, amendment 3B will adjust the dosing for new APEC1621C patients based on site of disease (CNS vs. non-CNS) and will allow for increased monitoring of T-LBL/ALL (see [Section 5](#) and [Section 6.2](#)). Based on the pediatric phase I trial of lower Tazemetostat exposures in children receiving 520mg/m², and one patient in this cohort receiving prolonged benefit, 520mg/m² was chosen for patients not requiring higher, CNS-penetrant doses to limit exposures and potential secondary malignancies.

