5.0 TREATMENT PROGRAM

5.1 Overview of Treatment Plan

For patient(s) enrolled pre-amendment #3B:

Day 1-28	Day 28
Tazemetostat 1200 mg/m²/dose (Orally, twice daily)	Evaluation

For patient(s) enrolled post-amendment #3B:

	Day 1-28	Day 28
Patients without CNS involvement	Tazemetostat 520mg/m²/dose (Orally, twice daily)	Evaluation
Patients with CNS involvement	Tazemetostat 1200 mg/m²/dose (Orally, twice daily)	Evaluation

Tazemetostat will be administered as a liquid suspension at a dose of 520 mg/m²/dose orally, twice daily (for patients without any CNS involvement); or 1200 mg/m²/dose orally twice daily (for patients with CNS involvement) (based on disease location per above table); without regard to meals with no less than 8 hours between each dose. For patient(s) enrolled pre-amendment #3B Tazemetostat will be administered orally at the MTD and recommended phase 2 dose (RP2D) of 1200 mg/m²/dose BID. If vomiting occurs after taking oral suspension formulation, the dose should NOT be repeated and the next dose should be administered at the regularly scheduled time. See [Section 9.1.6](#) and [Appendix](#)

[IV](#) for additional oral suspension administration and preparation instructions. See [Appendix V](#) for treatment roadmap.

Therapy will be discontinued if there is evidence of progressive disease or drug related dose-limiting toxicity that requires removal from therapy ([Section 6.0](#)). Therapy may otherwise continue for up to 2 years provided the patient meets the criteria for starting subsequent cycles ([Section 5.2](#)) and does not meet any of the criteria for removal from protocol therapy criteria ([Section 10.0](#)).

A cycle of therapy is considered to be 28 days. A cycle may be repeated up to a total duration of therapy of 2 years (maximum 26 cycles).

All patients with CNS involvement enrolled after AMD#3 will be treated at the established pediatric MTD/RP2D which is 1200 mg/m²/dose BID. All patients without any CNS involvement patients enrolled after AMD#3 will be treated at the lower starting dose of 520mg/m²/dose BID. (See [Section 6.1](#) and [Section 6.2](#)).

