6.1 Dose Modification for Patients Newly Diagnosed with T-LBL/T-ALL

- If a new case of T-LBL/T-ALL occurs in patients at the dose level > 520 mg/m² then the patient will be discontinued from treatment, a case assessment will be conducted to better understand the event, and enrollment will be suspended.
- If a new case of T-LBL/T-ALL occurs at ≤ 520 mg/m² or less than 1 year on study treatment, the patient will be discontinued from treatment and a case assessment will be conducted to better understand the event. Enrollment will be suspended and risk/benefit of the drug will be assessed to decide whether to continue the study or not.

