If ≥ 3 patients in the primary cohort with the same histology show signs of objective response (CR/PR according to the response criteria in [Section 12.3](#)), a histology-specific biomarker positive expansion cohort will open after the primary cohort is completed to up to 7 evaluable patients for a total sample size of 10 evaluable biomarker positive patients with that histology. This will allow us to estimate more precisely the activity in biomarker positive patients of that histology. See [Appendix VI](#) for a list of target tumor histologies/types.

We will open up to 3 such expansion cohorts for biomarker positive patients (i.e., if 3 histologies have ≥ 3 responses, we will open a total of 3 expansion cohorts as described above). Note that this can only happen if the response rate in the primary cohort is at least 45% (9/20) and there cannot be more than 21 additional evaluable patients in total for these expansion cohorts.

11.4 **Methods of Analysis**

Response criteria are described in [Section 12](#). A responder is defined as a patient who achieves a best response of PR or CR on the study. Response rates will be calculated as the percent of evaluable patients who are responders, and confidence intervals will be constructed using the Wilson score interval method.⁹ Decision making for A'Hern design cohorts will follow rules described above.

Toxicity tables will be constructed to summarize the observed incidence by type of toxicity and grade. A patient will be counted only once for a given toxicity for the worst grade of that toxicity reported for that patient. Toxicity information recorded will include the type, severity, time of onset, time of resolution, and the probable association with the study regimen.

11.5 **Evaluability for Response**

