Any eligible patient who is enrolled and receives at least one dose of protocol therapy will be considered evaluable for response. Any patient who receives non-protocol anti-cancer therapy during the response evaluation period will be considered a non-responder for the purposes of the statistical rule, unless they show an objective response prior to receiving the non-protocol anti-cancer therapy (in which case they will be considered a responder). Patients who demonstrate a complete or partial response confirmed by central review will be considered to have experienced a response. When opening expansion cohorts, the evaluation period for determination of best response will be 6 treatment cycles. All other patients will be considered non-responders. Patients who are not evaluable for response evaluation may be replaced for the purposes of the statistical rule. All patients considered to have a response (CR or PR) must have imaging studies reviewed centrally at the COG. Centers will be notified by the COG about requests for scans of patients with stable disease. Preliminary assessment of activity using institutionally provided tumor measurements will be entered into CDUS quarterly. The central review by COG will be provided as the final reviewed assessment of response when such becomes available.

11.6 **Evaluability for Toxicity**

All eligible patients who receive at least one dose of protocol therapy will be considered in the evaluation of toxicity.

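### Toxicity is tabulated only as crude incidence over all treated patients, so the report will not show how many were exposed long enough to be at risk of late events such as secondary malignancy

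*Combined protocol and SAP*

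**What the plan says.** Section 11.4 (Methods of Analysis) gives the toxicity analysis in three sentences. The summary measure is a crude frequency: "Toxicity tables will be constructed to summarize the observed incidence by type of toxicity and grade". The counting rule comes next: "A patient will be counted only once for a given toxicity for the worst grade of that toxicity reported for that patient". The last of the three lists the data to be collected: "Toxicity information recorded will include the type, severity, time of onset, time of resolution, and the probable association with the study regimen". Section 11.6 sets the population: "All eligible patients who receive at least one dose of protocol therapy will be considered in the evaluation of toxicity". No person-time rate, time-to-onset summary or cumulative incidence of toxicity is specified. Kaplan-Meier estimation appears only for PFS (Section 11.7).

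Exposure varies widely. Section 5.1 says "Therapy may otherwise continue for up to 2 years", with a maximum of 26 cycles of 28 days.

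On T-cell lymphoma, Section 2.7 reports that "one child developed T-cell lymphoblastic lymphoma (T-LBL) after receiving tazemetostat for 14 months". It adds, of all trials of the drug to that date, that "this is the only case of T-cell lymphoma that has occurred out of a total of 79 children enrolled". Section 6.1 mentions time on treatment in one of its two T-LBL/T-ALL rules ("less than 1 year on study treatment"). Section 11.3.1 suspends accrual on a single secondary T-cell lymphoma at any time and names treatment duration among the items then to be reconsidered. Section 9.1.9 lists T-cell lymphoma and abnormal bone growth as adverse events of special interest, and notes that the latter has not been seen in clinical trials of the drug.

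**The concern.** A crude percentage treats a patient who stopped after two months as fully observed for an event that may need a year or more of exposure. If few patients stay on drug that long, a small percentage, or a zero, over all treated patients says little about them. They are also the patients most likely to be benefiting.

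Two uses of the data are at stake. One is the report on secondary aim 1.2.2 (tolerability). The other is the reconsideration of duration under Section 11.3.1 after a case, which needs to know how many patients had reached that exposure. Onset times are recorded, but no stated analysis uses them.

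**Working it through.** **1. The plan's own figures.** The documents give no numerical toxicity target, so the sample size sets the denominator. For N = 20 and at least 3 responses, the exact binomial gives P(X ≥ 3 | 5%) = 0.0755, under the 10% ceiling, and P(X ≥ 3 | 25%) = 0.909, against a stated 90%. Adding the 21 possible expansion patients gives (20 + 21)/0.85 = 48.2, rounded up to the stated 49. These figures reproduce. The evaluable denominator therefore runs from 20 to 41.

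**2. Zero cases is the likelier outcome.** The earlier pediatric proportion is 1/79 = 1.27% (95% CI 0.03 to 6.9%), itself a crude figure. If it carried over, the chance of no case would be (78/79)^20 = 77.5% in 20 patients and (78/79)^41 = 59% in 41. The table then has to be read as a bound.

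**3. What a zero means.** The one-sided 95% upper bound is 1 − 0.05^(1/n):

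| Patients with relevant exposure | Upper bound |
|---|---|
| 41 | 7.0% |
| 20 | 13.9% |
| 10 | 25.9% |
| 5 | 45.1% |
| 3 | 63.2% |

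**4. How many might have long exposure.** The documents give no distribution of time on treatment. Assume it is exponential with median m months, so the share still on drug at 12 months is 0.5^(12/m):

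| Assumed median | Share at 12 months | Of 20 | Of 41 |
|---|---|---|---|
| 2 months | 1.6% | 0.3 | 0.6 |
| 4 months | 12.5% | 2.5 | 5.1 |
| 6 months | 25.0% | 5.0 | 10.3 |

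**5. How far a crude proportion could understate risk.** Suppose, for illustration only, a 10% risk by the end of maximum treatment (T = 26 × 28 days = 23.9 months) in a patient who stays on drug, with events only on treatment. Let λ = ln 2/m.
- Risk arising only after month 12: h = −ln(0.9)/(T − 12), and the expected crude incidence is the integral of h·exp(−h(t − 12))·exp(−λt) from 12 to T. For medians of 2, 4 and 6 months this is 0.04%, 0.5% and 1.4%. For 9 and 12 months it is 2.6% and 3.6%.
- Constant hazard: h = −ln(0.9)/T, and the expected crude incidence is h(1 − exp(−(h + λ)T))/(h + λ). For medians of 2, 4 and 6 months this is 1.3%, 2.4% and 3.5%.

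The understatement occurs in both cases and is larger if risk comes late.

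**6. A single patient-year rate would not cure this.** With 41 patients and a 4-month median, mean untruncated time is 4/ln 2 = 5.77 months. Total exposure to 24 months is 41 × 5.77 × (1 − 0.5^6)/12 = 19.4 patient-years. Exposure after month 12 is 41 × 5.77 × (0.125 − 0.0156)/12 = 2.2 patient-years. About 89% of the denominator is first-year exposure.

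**7. The suspension rule.** It triggers at a count of one and has no denominator, so none of the above changes when it acts.

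**The case against.** The strongest reply is that T-cell lymphoma is handled outside these tables. One case at any time suspends accrual, with DSMC notification and CTEP consultation (11.3.1). Section 6.1 requires a case assessment. Secondary malignancies after treatment are reportable through CTEP-AERS (13.6.2), and the DSMC meets at least every 6 months (14.4.1). This stands: a reader might infer that dilution weakens the safety rule, and it does not. It leaves open what is reported if no case occurs, and what exposure data inform the review if one does.

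A reader might also infer that T-LBL risk is known to depend on duration. The documents do not support that. Section 2.7 attributes the pediatric concentration of risk to epidemiology and pathophysiology, an active thymus and higher AUC. Section 2.2.2 describes rat lymphomas in 13-week studies, by dose and exposure. The one-year clause in Section 6.1 covers cases in the first year and does not single out late ones. One case at 14 months raises the possibility and no more.

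Two further points stand. Stopping drug does not end observation, because patients remain in follow-up on APEC1621SC (10.2), for a length these documents do not give. And aim 1.2.2 carries no hypothesis, so worst-grade tables suit most toxicities in a trial of this size.

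**Conclusion.** The point holds as a gap in descriptive safety reporting, of minor to moderate weight. For secondary malignancies and other possible late events, the planned table cannot show how many patients were exposed long enough to be at risk. It can therefore understate risk in those who stay on drug, or reassure too much about them. The size depends on time on treatment, which the documents do not give. If 5 of 20 patients reached long exposure, a zero count would bound their risk at about 45%, not 13.9%.

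A reader might go further and divide one case by the 5 or so of 41 patients expected on drug at 12 months, to claim a 20% risk. That figure should not be used. It needs an assumed 4-month median together with all three expansion cohorts, which require at least 9 of 20 responses (11.3.2). Over medians of 6 down to 2 months the same division runs from about 10% to an impossible value above 100%, and the 95% CI for 1/5 is 0.5 to 71.6%. Nor is early stopping by many patients a documented fact; it is plausible in relapsed disease, but assumed here.

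The primary endpoint and the suspension rule are unaffected.

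**What to change.** Keep the crude worst-grade table in Section 11.4. For secondary malignancies (including T-LBL/T-ALL) and other prespecified late-onset events such as abnormal bone growth, add the following, labelled descriptive and with confidence intervals for the estimates:

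- the distribution of time on treatment, and the numbers treated beyond 6, 12, 18 and 24 months (the last is in effect the number completing the permitted 26 cycles, 23.9 months without delays);
- time from first dose to onset for each event;
- cumulative incidence from first dose, with death as a competing event and numbers at risk shown.

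State whether time at risk includes off-treatment follow-up on APEC1621SC. If it is limited to time on drug, say how stopping treatment is handled. If every exit counts as a competing event and no one is censored, the curve ends at the crude proportion, so the numbers at risk carry the information. If stopping is treated as censoring, the estimate assumes that stopping is unrelated to the risk.

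If a patient-year rate is given, split it by exposure period, for example first year and after, because a single rate assumes a constant hazard.

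The cost is a little more programming, since onset times and dosing are already recorded. The intervals will be wide and should be shown as such.

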11.0 STATISTICAL AND ETHICAL CONSIDERATIONS

11.1 Sample Size

APEC1621C will require a minimum of 20 evaluable patients and a maximum of 49 patients, allowing for 15% inevaluability. Assuming an enrollment rate of 4-9 biomarker positive patients per year, the primary cohort of this subprotocol is expected to be completed within 2.7-6 years.

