11.3 Study Design

The primary cohort will employ a single stage A'Hern designs of N=20. Tazemetostat will be deemed worthy of further study in the relevant subset of patients (i.e. biomarker positive in any histology, biomarker positive in a particular histology, etc) if the decision rule is met. Operating characteristics are shown below.

Cohort	N	Decision Rule	Alpha	Power
Primary biomarker positive	20	≥ 3 responses	10%	90%

Per amendment 3B, Tazemetostat will be administered at a dose of 520 mg/m²/dose BID for patients without any CNS involvement; or 1200 mg/m²/dose BID for patients with CNS involvement. The response will be examined in the combined primary cohort consisting of patients with or without CNS involvement. Patients who enrolled pre-amendment #3B treated with at 1200 mg/m²/dose BID and meet evaluation criteria will also be counted in the evaluation.

Histology-specific biomarker positive expansion cohorts will, by definition, be deemed worthy of further study, since they will have at least 3 responses. The table below shows 90% confidence intervals (Wilson method) for a range of observable response rates.

Cohort Size	Observed Response Rate	90% Confidence Interval
10	30%	13% - 56%
10	40%	19% - 65%
10	50%	27% - 73%

11.3.1 Primary Cohort:

APEC1621C will evaluate a primary cohort of 20 mutation-matched ("biomarker positive") evaluable patients of any histology for the primary study aim of determining the objective response rate (CR/PR according to the response criteria in [Section 12.3](#)) to tazemetostat. Using an A'Hern design⁸ with alpha=10%, a sample of N=20 will provide 90% power to detect an improvement in response rate from 5%, if the treatment is ineffective, to 25% if the targeted therapy is sufficiently effective to warrant further study. If there are at least 3 responses out of 20 in the primary cohort, the biomarker/therapy match will be deemed a success.

If at any time, there is one occurrence of secondary T-cell lymphomas in patients exposed to tazemetostat, we will suspend the accrual and consider dose, schedule

or duration of treatment modification. The COG DSMC will be notified and CTEP consulted regarding the next steps to take with respect to the protocol.

11.3.2 **Histology-Specific Biomarker Positive Expansion Cohorts:**

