12.3.1 Definitions

12.3.1.1 Evaluable for objective response: Eligible patients who receive at least one dose of protocol therapy will be considered evaluable for response. Evaluable patients who demonstrate a complete or partial response confirmed by central review before receiving non-protocol anti-cancer therapy will be considered a responder. All other evaluable patients will be considered non-responders.

12.3.1.2 Evaluable Non-Target Disease Response: Eligible patients who have lesions present at baseline that are evaluable but do not meet the definitions of measurable disease and have received at least one dose of protocol therapy will be considered evaluable for non-target disease. The response assessment is based on the presence, absence, or unequivocal progression of the lesions.

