12.9 Best Response

Two objective status determinations of disease status, obtained on two consecutive determinations, separated by at least a 3 week time period, are required to determine the patient's overall best response. Two objective status determinations of CR before progression are required for best response of CR. Two determinations of PR or better before progression, but not qualifying for a CR, are required for a best response of PR. Two determinations of stable/no response or better before progression, but not qualifying as CR or PR, are required for a best response of stable/no response; if the first objective status is unknown, only one such determination is required. Patients with an objective status of progression on or before the second evaluations (the first evaluation is the first radiographic evaluation after treatment has been administered) will have a best response of progressive disease. Best response is unknown if the patient does not qualify for a best response of progressive disease and if all objective statuses after the first determination and before progression are unknown.

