12.9.1 Evaluation of Best Overall Response

The best overall response is the best response recorded from the start of the treatment until disease progression/recurrence (taking as reference for progressive disease the smallest measurements recorded since the treatment started). The patient's best response assignment will depend on the achievement of both measurement and confirmation criteria.

Table 5. Sequences of overall response assessments with corresponding best response.

1 st Assessment	2 nd Assessment	Best Response
Progression		Progressive disease
Stable, PR, CR	Progression	Progressive disease
Stable	Stable	Stable
Stable	PR, CR	Stable
Stable	Not done	Not RECIST classifiable
PR	PR	PR
PR	CR	PR
PR, CR	Not done	Not RECIST classifiable
CR	CR	CR

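### The responder definition for the primary endpoint is inconsistent: a single unconfirmed CR or PR can count under 11.5 but not under 11.4 with 12.9, and one such patient can decide the 3-of-20 rule

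*Combined protocol and SAP*

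**What the plan says.** All sections are in the combined protocol and SAP.

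- **11.4** defines a responder as a patient whose best response is PR or CR.
- **12.9** says how best response is reached: two consecutive determinations at least 3 weeks apart. For PR: "Two determinations of PR or better before progression, but not qualifying for a CR, are required for a best response of PR". CR needs two determinations of CR.
- **Table 5 in 12.9.1** labels a PR or CR with no second assessment "Not RECIST classifiable". A PR or CR followed by progression is progressive disease.
- **11.5, general sentence**, counts a CR or PR that central review has confirmed. It does not mention a second determination.
- **11.5, exception**, makes a patient given non-protocol anti-cancer therapy during the evaluation period a non-responder "unless they show an objective response prior to receiving the non-protocol anti-cancer therapy (in which case they will be considered a responder").
- **12.3.1.1** covers the same situation: "Evaluable patients who demonstrate a complete or partial response confirmed by central review before receiving non-protocol anti-cancer therapy will be considered a responder". Everyone else who is evaluable is a non-responder.
- **12.3** asks for a confirmatory scan one cycle after an objective response is first documented. There the term names the finding before confirmation.
- **11.3** sets the decision: "The primary cohort will employ a single stage A'Hern designs of N=20"; "If there are at least 3 responses out of 20 in the primary cohort, the biomarker/therapy match will be deemed a success".

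Neither 11.5 nor 12.3.1.1 refers to 12.9.

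**The concern.** The primary endpoint is a count compared with a threshold of 3, so the definition of one countable response carries the whole decision. The plan has one chain of rules that needs repetition in time (11.4 to 12.9) and another that needs only central review (11.5, 12.3.1.1). Central review is a second reading of the images. It does not supply a second determination at a later date, so a single PR scan can pass central review and still fail 12.9.

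The gap is widest in the 11.5 exception, which asks only for an objective response before the other therapy. A patient with a first PR who leaves protocol therapy before the confirmatory scan falls into this gap. If the conflict is left open, someone may have to choose the rule after seeing which patient it affects.

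**Working it through.** **1. The rules applied to the same evidence.** Take a patient with one PR scan, agreed by central review.

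| Rule | No second scan, no other therapy | Other therapy starts before a second scan |
|---|---|---|
| 11.4 with 12.9 and Table 5 | not a responder | not a responder |
| 11.5 general sentence, read alone | responder | see exception |
| 12.3.1.1, read alone | responder | responder, if confirmed before the therapy |
| 11.5 exception, read literally | does not apply | responder |

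Any eligible patient who has had one dose is evaluable (11.5, 12.3.1.1). This patient therefore stays in the denominator of 20 under every rule, and only the numerator moves.

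**2. The plan's own design.** Inputs from 11.3: N = 20, success at 3 or more responses, null rate 5%, alternative 25%, alpha 10%, power 90%.

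P(X ≥ 3 | p) = 1 − (1−p)^20 − 20p(1−p)^19 − 190p²(1−p)^18

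- p = 0.05: 1 − 0.3585 − 0.3774 − 0.1887 = 0.0755. Exact alpha is 7.55%, under the 10% ceiling.
- p = 0.25: 1 − 0.0032 − 0.0211 − 0.0669 = 0.9087. Power is 90.9%.

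The stated design reproduces, and N = 20 with a threshold of 3 is the smallest design that meets both limits.

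**3. One patient.** Two confirmed responders plus one patient with a single PR:

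- under 11.4 with 12.9: 2/20, failure, 90% Wilson interval 3.4% to 26.2%;
- under the literal 11.5 exception: 3/20, success, 90% Wilson interval 6.2% to 32.2%.

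**4. Sensitivity of the false-success probability.** Assume that 5% is the confirmed null rate and that unconfirmed but counted responses add q percentage points. The documents do not give q. The range is an assumption.

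| q (points) | counted null rate | P(3 or more of 20) |
|---|---|---|
| 0 | 5.0% | 7.55% |
| 0.5 | 5.5% | 9.4% |
| 0.64 | 5.64% | 10.0% |
| 1 | 6.0% | 11.5% |
| 2 | 7.0% | 16.1% |
| 3 | 8.0% | 21.2% |
| 5 | 10.0% | 32.3% |

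The crossing at 0.64 points corresponds to about one unconfirmed response for every eight confirmed ones under the null (5 / 0.64 = 7.8).

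**The case against.** The strongest reply is that the sections can be read together. The 11.5 exception is a rule about timing: the response must precede the other therapy. How a response is established is stated just before, in 11.4, through best response and hence 12.9. Section 11.5 also requires central imaging review of every CR or PR, makes that review the final assessment, and treats all other patients as non-responders.

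Much of this stands, and it rules out three stronger readings that a reader might infer:

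- **That 11.5 expressly accepts unconfirmed responses.** It does not. It is silent on a second determination.
- **That scoring depends on what treatment follows.** This appears only if 12.9 is applied to patients who stay on protocol and the literal exception to those who switch. Under one rule for both groups the difference goes: central review alone counts both, and 12.9 counts neither.
- **That the type I error exceeds 10%.** This rests wholly on an assumed frequency. If 5% already describes responses as counted, alpha stays at 7.55%. The probability of exactly two responses under the null is 18.9%, but that is not the probability of a reversal, which also needs a patient of this particular kind.

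The harmonised reading does not settle the matter. The text never says that 12.9 governs 11.5, 12.3 uses *objective response* for the unconfirmed finding, and central review cannot stand in for a second scan.

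**Conclusion.** The concern holds as a conflict in the definition of the primary endpoint. Whether central review of a single determination is enough, or two determinations are also needed, is unresolved for all patients. It is most exposed in the other-therapy exception.

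The consequence is concrete: with two confirmed responders, one patient separates failure from success. The literal exception can only add responders, so any error favours declaring success.

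The effect on the false-success probability cannot be estimated from the documents. It passes 10% only if unconfirmed responses add more than about 0.64 points to a confirmed null rate of 5%. The sample size, threshold and stated power are sound.

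**What to change.** Use one rule for all patients. Put it in place of the general responder sentence and the other-therapy exception in 11.5, and of the responder sentence in 12.3.1.1:

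*A responder is an evaluable patient with a best response of CR or PR under the two-determination rule in the text of Section 12.9, confirmed by central review, with both determinations made before any non-protocol anti-cancer therapy. All other evaluable patients are non-responders.*

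Changing only the exception would not be enough. Patients who switch would then need two determinations, while the general sentence would still ask the others for central review alone. The rule should cite the text of 12.9 because Table 5 lists only the first two assessments and scores stable disease followed by PR or CR as stable.

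At the same time, reconcile the 3-week interval in 12.9 with the 28-day confirmation interval in Table 1 (12.4.3). Section 8.1 lets studies be done up to 72 hours before the next cycle, so scans one cycle apart could fall 28 − 3 = 25 days apart. That satisfies 12.9 but not Table 1.

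The cost is a few sentences, with N and the threshold unchanged. The observed response rate may be slightly lower. If the 25% target was meant to include unconfirmed responses, power against it falls: should 10% of those fail confirmation (an assumption), the rate is 0.25 × 0.9 = 22.5% and power is 86.1%; at 20% it is 79.4%. The plan should therefore also say that 5% and 25% are confirmed rates, if that is what was intended.
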